The goal of this study (ARIOS), therefore, is to assess the safety and outcomes of infants and children who were exposed to retosiban or comparator in utero in the Phase III SPTL treatment studies and provide assurance that treatment is not associated with significant adverse outcomes in early childhood.

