1.3.1. Risk Assessment

This study is a follow-up safety study of infants and children exposed to treatment while in utero during their mother's participation in a Phase III SPTL treatment study of retosiban or comparator for SPTL. Infants and children enrolled in this study will not be administered any investigational product; therefore, there are no anticipated or known risks to the infants and children who participate in this safety study.

The intent of this study is to ensure there have been no unintended consequences to the infants and children from exposure to retosiban or comparator during their mother's participation in the Phase III clinical study of retosiban, specifically with respect to the following:

Potential Risk of Clinical Significance	Data/Rationale for Risk	Mitigation Strategy
Retosiban [e.g., GSK221149]		

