7.1.2. Loss to Follow-Up

Children for whom follow-up information is never obtained will be considered lost to follow-up. These cases will be tallied in the applicable sections of the study reports. All other cases with some follow-up data will be analyzed up to the length of child follow-up.

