## 4. ANALYSIS POPULATIONS

Population	Definition / Criteria	Analyses Evaluated
Infant Safety	
 
• All the infants whose mothers have been randomized and received retosiban or comparator in any of the Phase III treatment trials will be included in the Infant Safety analysis population.
 
• Of these mothers, the Infant Safety population includes the mother/infant pairs who enrolled into the ARIOS study, the mother/infant pairs who decline to consent to the study, and the mother/infant pairs whose fetus/neonates/infants has died prior to the enrolment of the study.
 
• Subjects will be analyzed according to their actual treatment in case this differs from their randomized treatment.
 
	
 
• Disposition
 
• All safety analyses
 

ARIOS Safety	
 
• Subset of the Infant Safety population for which the mother/infant pairs enrolled into the ARIOS study.
 
	
 
• Demographic
 
• All safety analyses
 

Data collected up to and including the 2-year assessments will be included in the descriptive summaries. Data collected beyond the 2-year assessment will be presented, but not included in the summaries.

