### 7.2. Safety Analyses

All safety summaries will be performed for both populations as defined in Section 4. A listing of all safety data will be presented.

The primary objective of the planned analysis will be to use descriptive statistics to describe the safety and morbidity and mortality outcomes of children exposed to treatment during the Phase III SPTL studies investigating retosiban or comparator for the treatment of SPTL up to 24 months chronological age. The endpoints to be descriptively summarized are those described in Section 2.2. Descriptive statistics will be calculated by treatment group and/or time (up to 24 months chronological age), where appropriate.

For binary outcomes, all summary tables will include the number and percentage of subjects with the response/event. All summary tables will include N for each group (i.e., the total number of subjects in each treatment group).

The focus will be on collecting the safety outcomes as defined in the objectives (e.g., death) and serious AEs (SAEs), including congenital anomalies.

Nonserious AEs will not be tracked. All SAEs and safety outcomes will be followed until resolution, stabilization, or loss to follow-up.

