## **7.2.3. Neurodevelopment Assessment at 9, 18, and 24 months**

Neurodevelopment will be assessed by determining the proportions of infants diagnosed with developmental delays listed below at 9, 18, and 24 months of age, corrected for prematurity.

Endpoints related to Ages and Stages Questionnaire version 3 (ASQ-3) score and developmental evaluation described in Section 2.2 will be descriptively summarized at 9, 18, and 24 months by treatment group. For subjects with an ASQ-3 score in the black zone ( $\geq 2$  standard deviation [SD] below the mean) for any domain and referred for development evaluation, number of infants and percentage with Bayley Scales of Infant Development 3rd edition (BSID-III) and non-BSID-III results will be summarized. For subjects with an ASQ-3 score in the black zone for any domain, referred for development evaluation, but no assessment done, reason of no assessment done will be summarized. In addition to endpoints described in Section 2.2, number of infants and percentage with moderate or severe developmental delay using non BSID-III score will be summarized.

For BSID-III score, scaled scores for cognitive, receptive communication, expressive communication, fine motor, and gross motor will be derived from the subtest total raw scores and range from 1–19, with a mean of 10 and an SD of 3. Language composite scores will be derived from sums of receptive communication and expressive communication scaled scores. The composite score will be scaled to a metric with a mean of 100 and an SD of 15, and range from 40–160.

Endpoints related to Modified Checklist for Autism in Toddlers Revised with Follow-Up (M-CHAT-R/F) described in Section 2.2 will be descriptively summarized at 18, and 24 months by treatment group.

Endpoints related to Child Behavior Checklist for Ages 1.5 to 5 (CBCL/1.5-5) and cerebral palsy in Section 2.2 will be descriptively summarized at 24 months by treatment group.

Neurodevelopment assessment data will be presented in listings.

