### 10.6.2. Handling of Missing Data

Element	Reporting Detail
General	

• Missing data occurs when any requested data is not provided, leading to blank fields on the collection instrument :

[1] These data will be indicated by the use of a “blank” in subject listing displays.

[2] Answers such as “Not applicable” and “Not evaluable” are not considered to be missing data and should be displayed as such.

• For disposition and demographic data, no imputation will be done.

• For safety and neurodevelopment data, it will be assumed that the events of interest did not occur.

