### 10.8.3. Safety Tables

Safety Tables					
No.	Population	IDSL / TST ID / Example Shell	Title	Programming Notes	Deliverable [Priority]
Adverse Events					
10.5	Infant Safety		Summary of Infant Serious Adverse Events		
20.5	ARIOS Safety		Summary of Infant Serious Adverse Events		
Neurodevelopment Assessments					
10.7	Infant Safety		Neurodevelopment Assessments (ASQ-3 and BSID-III scores) at 9, 18 and 24 Months		
20.7	ARIOS Safety		Neurodevelopment Assessments (ASQ-3 and BSID-III scores) at 9, 18 and 24 Months		
10.8	Infant Safety		Neurodevelopment Assessments (CBCL/1.5-5. M-CHAT-R/F, Cerebral Palsy or Behavioral Specialist) at 18 and 24 Months		
20.8	ARIOS Safety		Neurodevelopment Assessments (CBCL/1.5-5. M-CHAT-R/F, Cerebral Palsy or Behavioral Specialist) at 18 and 24 Months		
10.9	Infant Safety		Neurodevelopment Impairment at the End of Study (24 Months)		
20.9	ARIOS Safety		Neurodevelopment Impairment at the End of Study (24 Months)		
Congenital Anomaly					
10.10	Infant Safety		Summary of Congenital Anomaly		
20.10	ARIOS Safety		Summary of Congenital Anomaly		

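### SAP 10.6.2 counts missing safety and neurodevelopment data as no event, which can only lower printed event rates and does so unequally across arms in the primary population

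*Protocol*

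**What the plan says.** **Missing data.** SAP 10.6.2 makes no imputation for disposition and demography. For the outcomes that matter it does: "For safety and neurodevelopment data, it will be assumed that the events of interest did not occur". It defines missing broadly, as any requested item left blank.

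**Statistics and denominator.** Binary endpoints get a number and a percentage (Protocol 8.3.5.1.1; SAP 7.2). SAP 7.2 adds: "All summary tables will include N for each group (i.e., the total number of subjects in each treatment group". SAP 10.4.3 lists N, n, frequency and % for categorical data. Neither section says that the percentage is taken on infants assessed.

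**Populations.** All safety summaries are run twice. The primary Infant Safety population includes infants whose parents declined ARIOS and those who died before enrolment. ARIOS Safety is the "Subset of the Infant Safety population for which the mother/infant pairs enrolled into the ARIOS study". Tables 10.7 to 10.9 report neurodevelopment for the first, and 20.7 to 20.9 for the second.

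**Known gaps.** SAP 7.2.3 foresees infants in the ASQ-3 black zone who are "referred for development evaluation, but no assessment done, reason of no assessment done will be summarized". SAP 7.2.5 then reports the 24-month impairment composite as a number and percentage.

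**Protocol on losses.** Protocol 7.1.2 tallies infants with no follow-up as lost, and continues: "All other cases with some follow-up data will be analyzed up to the length of child follow-up".

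**Background goal.** Protocol 1.2, like the Protocol Summary, wants the study to "provide assurance that treatment is not associated with significant adverse outcomes in early childhood".

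**The concern.** In an efficacy trial, counting a missing response as failure is usually conservative. Here the coding runs the other way: a missing harm is recorded as no harm. The printed figure is a lower bound presented as an estimate.

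Three groups are affected:

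- enrolled infants whose questionnaire at a given age is missing;
- infants who screened in the black zone and were referred but never evaluated. They are among the likeliest true cases, yet they count as having no BSID-III impairment in the composite;
- in Tables 10.7 to 10.9, infants who never enrolled in ARIOS, for whom no ARIOS questionnaire can exist.

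The third group is probably spread unevenly over the arms. If so, the rule not only lowers rates but can also create or hide a difference in the two comparisons the SAP calls primary, retosiban versus placebo and retosiban versus atosiban.

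**Working it through.** **Inputs**

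- Enrolled in ARIOS (Protocol Appendix 1, justification for Amendment 2): 49 retosiban, 43 atosiban, 6 placebo.
- Group sizes in the treatment trials (Protocol 1.1.1): NEWBORN-1, 10 retosiban and 13 placebo; ZINN, 50 retosiban and 47 atosiban.
- Assumed, because the documents give no figures: that the group sizes are the treated numbers, a true rate of 10%, the number assessed, and the case counts.

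**The plan's own figures.** 49 + 43 + 6 = 98, and 98 / (900 + 330) = 98 / 1230 = 7.97%, the stated 8%. Also 10 + 13 = 23 and 50 + 47 = 97, which match the enrolment given in the Protocol Summary.

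**Infant Safety tables.** The share with no ARIOS data is (treated − enrolled) / treated. If every enrolled infant is fully assessed, the printed rate at a true 10% is 10% × enrolled / treated.

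| Arm | Treated (assumed) | Enrolled | No ARIOS data | True 10% prints as |
|---|---|---|---|---|
| Retosiban | 10 + 50 = 60 | 49 | 11/60 = 18% | 8.2% |
| Atosiban | 47 | 43 | 4/47 = 9% | 9.1% |
| Placebo | 13 | 6 | 7/13 = 54% | 4.6% |
| All comparators | 47 + 13 = 60 | 49 | 11/60 = 18% | 8.2% |

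With no true difference, retosiban would show 8.2 / 4.6 = 1.8 times the placebo rate and 8.2 / 9.1 = 0.9 times the atosiban rate. On these counts the pooled comparison is undistorted by coincidence, since 49 of 60 is the share enrolled on both sides.

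**ARIOS Safety tables.** Assume 39 of 49 retosiban infants are assessed and 3 are cases. On infants assessed, 3/39 = 7.7%. Under the rule, with N as denominator, 3/49 = 6.1%.

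**The composite.** Assume instead 3 cases and 3 black-zone infants without an evaluation among 49. The true figure can lie anywhere from 3/49 = 6.1% to 6/49 = 12.2%. The rule gives only 6.1%.

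**What zero events would mean.** The exact (Clopper-Pearson) two-sided 95% upper limit is 1 − 0.025^(1/n): 7.3% for n = 49, 8.2% for n = 43 and 45.9% for n = 6. With only 39 retosiban infants assessed it is 9.0%, although under the rule the table would still show 0/49.

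**The case against.** **The denominator is not stated outright.** This is correct. Table shells and derivations are in separate documents, and SAP 10.4.3 lists both N and n. N as denominator is an inference from SAP 7.2 and the no-event rule, so the printed figures above depend on it. The rule itself is explicit.

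**Non-assessment is not hidden.** SAP 6.2 tabulates how many infants reach 9, 18 and 24 months, SAP 7.2.3 summarises BSID-III and other results and the reasons for no evaluation, and listings show individual infants. This lets a careful reader see the gap. It does not correct the percentage in Tables 10.9 and 20.9.

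**Protocol 7.1.2 is not contradicted.** It deals with tallying losses and using available data, and sets no denominator. The SAP rule fits poorly with it, but the two do not conflict outright.

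**A reader might infer that the plan fails because it promises assurance without intervals.** Besides the Rationale wording, Protocol 1.3.1 says: "The intent of this study is to ensure there have been no unintended consequences to the infants and children". But these are background sentences. The objectives are to characterise, the analysis is descriptive, Amendment 2 removed the confidence intervals on purpose, and the protocol admits a greatly reduced sample. Absence of intervals is therefore a deliberate choice and not an error.

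**A reader might also infer that heavy drop-out by 24 months is documented.** It is not. The remark that drop-out would increase belongs to the argument against five years of follow-up and gives no 24-month figure.

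**Conclusion.** The point holds for the missing-data rule. SAP 10.6.2 is current text, and it makes each safety and neurodevelopment percentage a lower bound. It matters most in the primary Infant Safety tables, where a common 10% rate would print as 8.2%, 9.1% and 4.6%. That distorts the comparison with placebo in particular, here to the apparent disadvantage of retosiban. Within ARIOS Safety the effect is more modest, 6.1% against 7.7% in the example.

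These sizes rest on the Protocol 1.1.1 counts being treated numbers, on N being the percentage denominator, and on assumed rates, cases and missingness. The direction of the effect within an arm does not depend on the assumed rates or counts.

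The documents do not support the broader claim that the study sets out to prove safety and cannot. The sample is too small for a conclusion of no harm, above all with 6 placebo infants, but a descriptive plan does not require one. The change should be made; it is not grounds to reject the analysis.

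**What to change.** 1. **Neurodevelopment endpoints.** Delete the no-event assumption. Show the number assessed at each age and use it as the percentage denominator. Report endpoints collected in ARIOS on infants with ARIOS data, and do not count never-enrolled infants as non-cases in Tables 10.7 to 10.9.
2. **24-month composite (Tables 10.9 and 20.9).** Give infants with unresolved components their own row, with any non-BSID-III result reported there. A BSID-III that was never triggered by the ASQ-3 is not unresolved. Print the lower bound (all unresolved as non-cases) and the upper bound (all as cases). Avoid a single percentage that admits incomplete infants only when they are positive.
3. **SAEs, new chronic conditions and anomalies found in ARIOS.** Show per arm the number followed, the follow-up time and the number reaching 24 months, in line with Protocol 7.1.2. Having completed one early questionnaire should not make an infant a 24-month non-case. Keep anomalies from the treatment studies and deaths before enrolment reported for Infant Safety.
4. **Optional.** Add exact 95% intervals per arm for the few key endpoints, and a sentence in the study report that these numbers, 6 placebo infants above all, cannot support a conclusion of no harm. Rewording the goal in the Protocol Summary, 1.2 and 1.3.1 is desirable but not essential.

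**Cost.** Items 1 to 3 need a SAP revision before unblinding, a short definition of assessed for each endpoint, and modest programming. No new data are needed. Only the rewording in item 4 would need a protocol amendment with ethics review. The downside is that denominators will differ by endpoint and rates will look slightly less favourable.

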1.3. Benefit:Risk Assessment

Summaries of findings from both clinical and nonclinical studies conducted with GSK221149 can be found in the IB and the Phase III SPTL treatment clinical study

reports. The following section outlines the risk assessment and mitigation strategy for this protocol.

1.3.1. Risk Assessment

This study is a follow-up safety study of infants and children exposed to treatment while in utero during their mother's participation in a Phase III SPTL treatment study of retosiban or comparator for SPTL. Infants and children enrolled in this study will not be administered any investigational product; therefore, there are no anticipated or known risks to the infants and children who participate in this safety study.

The intent of this study is to ensure there have been no unintended consequences to the infants and children from exposure to retosiban or comparator during their mother's participation in the Phase III clinical study of retosiban, specifically with respect to the following:

Potential Risk of Clinical Significance	Data/Rationale for Risk	Mitigation Strategy
Retosiban [e.g., GSK221149]		
Fetal exposure through placental transfer	
For both NEWBORN-1 and ZINN, cord blood samples were requested from subjects who delivered at the investigative center within 12 hours after discontinuation of study drug. Samples were only analyzed for subjects randomized to retosiban. A total of 4 cord samples were collected within NEWBORN-1 (3 placebo: 1 retosiban) and 27 within ZINN (12 retosiban: 15 atosiban). Within both studies, only 1 cord blood sample tested positive for retosiban at a concentration of 1.9 µg/L. The 1.9 µg/L is approximately 0.006x to 0.01x the cord blood concentrations that were observed in the pregnant monkey toxicity studies (cord blood concentrations = 159 to 313 µg/L). There were no adverse effects observed in the offspring in monkey studies, where growth and development included a full assessment of reflexive behaviors, infant ECG and blood chemistry were analyzed. Furthermore, a rat post-natal study starting in juvenile rats that were 1 day old did not show any adverse effects on growth and development, including neurobehavior and reproductive assessments at exposure levels that were approximately 800-fold of what was observed in the cord blood (gender averaged Cmax = 1535 µg/L). Day 1 old rats were used in this study as they were developmentally similar to late third term human fetuses. The overall animal data indicate that potential risk for a fetus exposed gestationally to retosiban is negligible.
	
Analysis of maternal blood and cord blood samples was performed to test for levels of retosiban in women who delivered at an investigative center within 12 hours of the completion of study treatment infusion as part of the Phase III SPTL treatment studies. Surveillance for signals indicating adverse fetal or neonatal effects with in utero exposure to retosiban will be performed throughout this study. Infants exposed to retosiban in utero will be followed for up to 24 months in this study to assess safety and neurodevelopmental outcomes.

Potential Risk of Clinical Significance	Data/Rationale for Risk	Mitigation Strategy
Retosiban [e.g., GSK221149]		
Neonatal exposure via breast milk	
Positive breast milk samples were detected within 1 maternal subject in NEWBORN-1 and 1 subject in ZINN, with the highest concentration being 0.36 µg/L. Assuming a standardized milk consumption of 0.150 L/kg/day (the mean milk intake of a fully breast-fed 2-month old infant [Begg, 1999; Bennett, 1988; Hagg, 2000; Kristensen, 1999]), the worst-case dose of retosiban that a breast-fed child would be exposed to is 0.54 µg/kg/day (3.6 µg/L x 0.15 L/kg/day). This is approximately 0.5% of the human dose. This is the worst-case scenario because the mother is not being administered retosiban post-partum during the lactation period, and retosiban is cleared rapidly, which would rapidly diminish the amount retosiban present circulation and in the milk. Furthermore, based on body surface area, this potential infant dose is greater than 8000-fold, the dose where no adverse effects were seen in growth and development in the rat post-natal development study (rat post-natal development study NOAEL = 30 mg/kg/day; human equivalent dose = 4800 µg/kg/day). The potential lactational dose of retosiban that would therefore pose any significant risk to a newborn is negligible.
	
Breast milk/colostrum samples were collected for measurement of retosiban when delivery occurred and lactation had started within 12 hours of receiving study treatment infusion as part of the Phase III SPTL treatment studies. Infants exposed to retosiban via breast milk will be followed for up to 24 months in this study to assess safety and neurodevelopmental outcomes.

ECG = electrocardiogram; NOAEL = no-observed-adverse-effect-level; SPTL = spontaneous preterm labor.

1.3.2. Benefit Assessment

Babies born prematurely are at risk for death, short-term medical complications, long-term disabilities, and developmental problems; these risks are inversely related to gestational age. Although babies born before 32 weeks have the greatest risk for death and poor health outcomes [Saigal, 2008; Lundqvist, 2009; Matthews, 2010], late preterm infants (defined as 34^{0/7} to 36^{6/7} weeks) are now known to carry a higher risk of morbidity and mortality than term infants [Engle, 2007]. Approximately 40% to 45% of preterm births are preceded by SPTL; the remainder is associated with preterm premature rupture of membranes and clinical indications for delivery [Romero, 2000; Goldenberg, 2008].

Treatment of SPTL is aimed at improving outcomes for the child and should be considered in women for whom a delay in delivery will provide benefit to the newborn. Tocolytic therapy is currently recommended for short-term delay of delivery in order to administer antenatal corticosteroids, which reduce the risks for neonatal mortality and morbidity, and transfer the mother to a neonatal specialized care unit. However, there is no evidence that current tocolytic regimens improve neonatal or infant outcomes beyond the effect of antenatal corticosteroids [RCOG, 2011; ACOG, 2012; Roos, 2013].

Given the inverse relationship between the risks for prematurity complications and gestational age at birth, the development of a treatment that significantly prolongs pregnancy in women with SPTL would be invaluable if associated with improved perinatal outcomes. Results from the Phase II study OTA105256 offer hope that retosiban may prolong pregnancy to such a degree that perinatal outcomes could be favorably affected [Thornton, 2015]. However, the results from the Phase III interventional studies did not provide compelling evidence that retosiban could prolong time to delivery of retosiban relative to placebo or atosiban, but because of the low enrollment numbers and inadequate statistical power, results should be interpreted with caution.

The benefit to infants and children participating in this study is the focus on following morbidity and neurodevelopment for up to 24 months following exposure to retosiban or comparator medication. Participating infants and children will have the benefit of access to developmental screening (Ages and Stages Questionnaire-3 [ASQ-3], Child Behavior Checklist for Ages 1.5 to 5 [CBCL/1.5–5], and the Modified Checklist for Autism in Toddlers–Revised with Follow-Up [M-CHAT-R/F]), which may not be routinely provided and will allow parents/legal guardians to monitor and track the child's developmental milestones in a formalized manner. In addition, screening results may be shared with the child's physician (HCP or other) as requested by the parent/legal guardian. In the event a potential issue is identified and further follow-up is warranted, the child will be referred to developmental specialists/qualified assessors for further evaluations as part of this study. In this manner, neurodevelopmental issues may be identified earlier than would have been normally.

